## 8.1.2 Post Treatment Follow-up

Post treatment follow-up is of critical importance and is essential to preserving participant safety and the integrity of the study. Participants who discontinue study treatment must continue to be followed for safety follow-up as required and in line with Section 5.1.5.

## 8.2 Discontinuation from the Study

Participants who request to discontinue study treatment will remain in the study and must continue to be followed for protocol specified follow-up procedures. The only exception to this is when a participant specifically withdraws consent for any further contact with him/her or persons previously authorized by participant to provide this information.

- Participants should notify the investigator of the decision to withdraw consent from future follow-up in writing, whenever possible.
- The withdrawal of consent should be explained in detail in the medical records by the investigator, whether the withdrawal is from further treatment with study treatment only or also from study procedures and/or post treatment study follow-up, and entered on the appropriate CRF page.
- In the event that vital status (whether the participant is alive or dead) is being measured, publicly available information should be used to determine vital status only as appropriately directed in accordance with local law.
- If the participant withdraws consent for disclosure of future information, the sponsor may retain and continue to use any data collected before such a withdrawal of consent.

#### 8.2.1 Study Termination

BMS reserves the right to terminate the study at any time for reasons including but not limited to the following: safety concerns, termination of drug development, lack of efficacy, and lack of meeting study objectives/endpoints.

#### 8.3 Lost to Follow-up

• All reasonable efforts must be made to locate participants to determine and report their ongoing status. This includes follow-up with persons authorized by the participant.

• Lost to follow-up is defined by the inability to reach the participant after a minimum of **three** documented phone calls, faxes, or emails as well as lack of response by participant to one registered mail letter. All attempts should be documented in the participant's medical records.

- If it is determined that the participant has died, the site will use permissible local methods to obtain date and cause of death.
- If investigator's use of third-party representative to assist in the follow-up portion of the study has been included in the participant's informed consent, then the investigator may use a Sponsor retained third-party representative to assist site staff with obtaining participant's contact information or other public vital status data necessary to complete the follow-up portion of the study.
- The site staff and representative will consult publicly available sources, such as public health registries and databases, in order to obtain updated contact information.
- If after all attempts, the participant remains lost to follow-up, then the last known alive date as determined by the investigator should be reported and documented in the participant's medical records.

#### 9 STUDY ASSESSMENTS AND PROCEDURES

- Study procedures and timing are summarized in the Schedule of Activities (See Section 2).
- Protocol waivers or exemptions are not allowed.
- All immediate safety concerns must be discussed with the Sponsor immediately upon occurrence or awareness to determine if the participant should continue or discontinue treatment.
- Adherence to the study design requirements, including those specified in the Schedule of Activities, is essential and required for study conduct.
- All screening evaluations must be completed and reviewed to confirm that potential participants meet all eligibility criteria before randomization. The investigator will maintain a screening log to record details of all participants screened and to confirm eligibility or record reasons for screening failure, as applicable.
- Procedures conducted as part of the participant's routine clinical management (eg, blood count) and obtained before signing of informed consent may be utilized for screening or baseline purposes provided the procedure meets the protocol-defined criteria and has been performed within the timeframe defined in the Schedule of Activities.

Additional measures, including non-study required laboratory tests, should be performed as clinically indicated or to comply with local regulations. Laboratory toxicities (eg, suspected druginduced liver injury [DILI] enzyme evaluations) will be monitored during the follow-up phase via on site/local labs until all study treatment related toxicities resolve, return to baseline, or are deemed irreversible.

If a participant shows pulmonary-related signs (hypoxia, fever) or symptoms (eg, dyspnea and cough) consistent with possible pulmonary AEs, the participant should be immediately evaluated

to rule out pulmonary toxicity, according to the suspected pulmonary toxicity management algorithm in the BMS-936558 (nivolumab) IB.

Some of the assessments referred to in this section may not be captured as data in the eCRF. They are intended to be used as safety monitoring by the treating physician.

Additional testing or assessments may be performed as clinically necessary or where required by institutional or local regulations.

#### 9.1 Safety Assessment

Safety assessments will be based on reported AE and the measurement results of vital signs including oxygen saturation, ECGs, physical examinations, and clinical laboratory tests. AEs will be coded using the most current version of Medical Dictionary for Regulatory Activities and the incidence of observed AEs will be tabulated and reviewed for potential significance and clinical importance. AEs will be assessed continuously during the study and for a minimum of 100 days after the last dose of study treatment. A local laboratory will perform the clinical laboratory tests and will provide reference ranges for these tests. Both AEs and laboratory tests will be graded using the NCI CTCAE v4.03.

Planned timepoints for all safety assessments are listed in the Schedule of Activities in Section 2.

## 9.1.1 Physical Examinations

A full physical exam will be obtained during select times during study participation. Refer to the Schedule of Activities for timing of assessments in Section 2.

## 9.1.2 Vital signs

Pre and post dose vital signs will be obtained during the dosing visits. Vital signs including oxygen saturation will be obtained during select times during study participation. Refer to the Schedule of Activities for timing of assessments in Section 2.

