		C (	ycle 1 28 d)	1			Cycl (28	le 2 d)		Cyc (28	ele 3 d)		C	ycle 4 28 d)	1		Cyc + (28	le 5 8 d)	EOT a,b	Notes
Procedure	D1	D2	2 80	D15°	D22°	D1°	D2°	D8	D15°	D1°	D15°	D1c	D2°	$\mathbf{D8}^{\mathbf{c}}$	D15c	D22°	D1¢	D15		
ECG	X			X		X			X	X		X					X		X	12-lead ECGs should be recorded after participant has been supine for at least 5 minutes.

Table 2-4: On-treatment Procedural Outline (Cohorts 1B4 through 1B6 - BMS-986253 Q2W and Nivolumab Q4W)

			ycle 28 d)				Cycl (28			Cyc (28				ycle 4 28 d)			Cyc + (28		EOT a,b	Notes
Procedure	D1	D2	$\mathbf{D8}^{\mathbf{c}}$	D15°	D22°	$\mathbf{D1}^{\mathfrak{c}}$	$D2^{c}$	D8	D15°	D1°	D15°	D1°	D2°	$\mathbf{D8}^{\mathrm{c}}$	D15°	D22°	D1 c	D15		
Laboratory Testing	Xe			X		X			X	X		X					X		X	See Section 9.1.4
Physical Examination (Complete)	X		X	X	X	X			X	X		X					X		X	Physical Examination (Complete)
Pregnancy Test (WOCBP)	X					X				X		X					X			Serum or urine pregnancy test must be performed (urine pregnancy test: minimum sensitivity 25 IU/L or equivalent units of hCG) within 24 hours prior to administration of study drug.
Thyroid Function Tests (TSH)	X*											X*					X*		X	*TSH to be done every 3rd cycle, ie, C1D1, C4D1, C7D1, etc. If TSH is abnormal, T3 and free T4 should be collected. Results should be examined by the investigator or appropriate designee within 48 hours of dose administration.

Date: 17-May-2024

Approved v8.0 930120018 9.0

Table 2-4: On-treatment Procedural Outline (Cohorts 1B4 through 1B6 - BMS-986253 Q2W and Nivolumab Q4W)

			ycle 28 d)				Cycl (28			Cyc (28				ycle 4 28 d)			Cyc + (2		EOT a,b	Notes
Procedure	D1	D2	D8c	D15°	D22°	D1¢	D2°	D8	D15°	D1°	D15°	D1°	$D2^{c}$	$D8^c$	D15°	D22°	D1°	D15		
Weight	X					X				X		X					X		X	
Vital Signs and Oxygen Saturations	X*	X	X	X	X	X*			X	X*	X	X*			X		X	X	X	Includes body temperature, respiratory rate, seated blood pressure, and heart rate. Blood pressure and heart rate should be measured after the participant has been resting quietly for at least 5 minutes. Consider alternate position(s) for vital sign collection. Obtain oxygen saturation at rest. *Pre- and post-dose vital signs on Day 1 of each cycle. Note: post dose vital signs are to be taken after BMS-986253 infusion AND after Nivolumab infusion.
Adverse Event Rep	orting																			

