Monitor for Nonserious Adverse Events	No	onserious AEs must be collected starting with the first dose of study drug and for a minimum of 100 days after discontinuing study treatment.																		

930120018 9.0

Protocol Amendment No.: 07

Date: 17-May-2024

Approved v%.0

Table 2-4: On-treatment Procedural Outline (Cohorts 1B4 through 1B6 - BMS-986253 Q2W and Nivolumab Q4W)

			ycle 28 d)				Cycl (28				ele 3 3 d)			ycle 4 28 d)			Cyc + (2	ele 5 8 d)	EOT a,b	Notes
Procedure	D1	D2	D8c	D15°	D22°	D1°	D2°	D8	D15°	D1°	D15°	D1°	$\mathbf{D2}^{\mathrm{c}}$	$\mathbf{D8}^{\mathrm{c}}$	D15°	D22°	D1c	D15		
Monitor for Serious Adverse Events	disco	ontinu	ing st	udy tı	reatme		ath d					en con							iys after study	
PK Assessments		See Section 9.5 for further details																		
Immunogenicity Assessments		See Section 9.5 for further details																		
Biomarker Assessments		See Section 9.5 for further details  See Section 9.8																		
Additional Research Sampling									Se	e Sect	ion 9.8	3.4								
Efficacy Assessments									S	ee Sec	tion 9.	4								
Body Imaging	occ	ur eve	ery 8 vithdra	weeks wal o	s (± 7 of cons	days), sent, de	startii eath, i	ng fro nitiat	om fir	st dose f anoth	e for th er anti		48 we r treat	eks, t ment	hen e	very nal a	12 wed nalysis	eks (± , whic		
Brain Imaging	P	Partici	pants	with	a histo							surveil See Se e			as cli	nical	ly indi	cated	at the	
Other: Bone Scan					Α	s clini	cally	indic	ated p	er loc	al stan	dards. S	See Se	ection	9.4.1					
Clinical Supplies																				
IRT Assignment	X																			Once eligibility has been confirmed, IRT assignment may be performed up to 3 days prior to study drug administration.

Date: 17-May-2024

Approved v8.0 930120018 9.0

Table 2-4: On-treatment Procedural Outline (Cohorts 1B4 through 1B6 - BMS-986253 Q2W and Nivolumab Q4W)

			ycle 1 28 d)				Cycl (28			Cyc (28				ycle 4 28 d)			Cycl + (28		EOT a,b	Notes
Procedure	D1	D2	$\mathbf{D8}^{\mathbf{c}}$	D15°	D22°	D1°	$D2^{c}$	D8	D15°	D1°	D15°	D1°	$D2^{c}$	$\mathbf{D8}^{\mathbf{c}}$	D15°	$D22^{c}$	D1°	D15		
Study Drug Admini	istratio	on																		Details regarding preparation and administration are provided in the pharmacy manual or training materials.
BMS-986253 Administration	X			X		X			X	X	X	X			X		X	X		BMS-986253 will be administered on day 1 and 15 of ALL cycles. See Section 7.1 for BMS-986253 dose administration.

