Brain Imaging	Participants with a	history of	brain metastas	sis should h	ave surveillance MRI as clinically indicated at the discretion of the investigator. See Section 9.4.1 .					
Other: Bone Scan			As c	linically inc	licated per local standards. See Section 9.4.1.					
Clinical Supplies										
IRT Assignment	X				Once eligibility has been confirmed, IRT assignment may be performed up to 3 days prior to study drug administration.					
Study Drug Adm	inistration				Details regarding preparation and administration are provided in the pharmacy manual or training materials.					

Abbreviations: C, Cycle; CT, computed tomography; d, days; D, Day; ECG, electrocardiogram; ECOG, Eastern Cooperative Oncology Group; EDC, Electronic Data Capture; EOI, end of infusion; EOT, end of treatment; hCG, human chorionic gonadotropin; IRT, Interactive Response Technologies; MRI, magnetic resonance imaging; PK, pharmacokinetic(s); SAE, serious adverse event; T3, triiodothyronine; T4, thyroxine; TSH, thyroid stimulating hormone; WOCBP, women of childbearing potential.

Protocol Amendment No.: 07

<sup>a For participants who complete all scheduled cycles of therapy, the EOT visit will be the same visit as the last scheduled and completed on-treatment visit and the start of the Week 1 Clinical/Safety Follow-up visit.

Protocol Amendment No.: 07

b For participants who do not complete all scheduled cycles of therapy, the EOT visit will be the next visit following the last study dose. If the EOT visit occurs 30 days or more after receipt of the last dose, then the EOT visit and Follow-up 1 visit can be completed at the same time.

<sup>c If multiple procedures are required at a single timepoint, safety assessments (ECGs, vital signs, and pulse oximetry) are a higher priority than PK/immunogenicity sampling.

Table 2-6: On-treatment Procedural Outline (Part 1C and Part 2 - BMS-986253 Q2W and Nivolumab and Ipilimumab Q3W)

Cycle 1 and 2 (42 d) Cycle 3 and Beyond (28 d)		EOT a,b	Notes								
	D1	D15	D22	D29	D36	DI	D15				
Safety Assessmen	Safety Assessments c										

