Vital Signs and Oxygen Saturations	X	X	X	X		X		X	Includes body temperature, respiratory rate, seated blood pressure, and heart rate. Blood pressure and heart rate should be measured after the participant has been resting quietly for at least 5 minutes. Consider alternate position(s) for vital sign collection. Obtain oxygen saturation at rest. *Pre- and post-dose vital signs on Day 1 of each cycle. Note: Post dose vital signs are to be taken after nivolumab infusion, ipilimumab infusion and BMS-986253 or placebo infusion.		
Weight	X		X			X		X			
Physical Examination (Complete)	X		X			X		X	Physical Examination (Complete)		
ECOG Performance Status	X		X			X			Appendix 5		
Concomitant Medication Assessments	X	X	X	X		X		X	Assess concomitant treatment during the study duration.		

Table 2-6: On-treatment Procedural Outline (Part 1C and Part 2 - BMS-986253 Q2W and Nivolumab and Ipilimumab Q3W)

Procedure			cle 1 ar (42 d)			Bey	3 and rond 3 d)	EOT a,b	Notes
	D1	D15	D22	D29	D36	D1	D15		
ECG	X		X*			х		X	Participants with no clinically relevant changes on ECGs at 6 months on treatment may discontinue routine ECGs.  See of ECGs.  * Required for Part 1C only.
Laboratory Testing	X		X			X		X	See Section 9.1.4  Only applicable for Part 1C: For HCC participants AFP
Pregnancy Test (WOCBP)	X					X		X	Serum or urine pregnancy test must be performed (urine pregnancy test: minimum sensitivity 25 IU/L or equivalent units of hCG) within 24 hours prior to administration of study drug.
Thyroid Function Tests (TSH)	X		X			X*			*TSH to be done on C3D1, C4D1, C5D1, and C6D1. TSH to be done every other cycle, after C6D1 (ie, C8D1, C10D1, etc). If TSH is abnormal, T3 and free T4 should be collected. Results should be examined by the investigator or appropriate designee within 48 hours of dose administration.

Date: 17-May-2024

Approved v 8.0 930120018 9.0

Table 2-6: On-treatment Procedural Outline (Part 1C and Part 2 - BMS-986253 Q2W and Nivolumab and Ipilimumab Q3W)

Procedure	Cycle 1 and 2 (42 d)  Cycle 3 and Beyond (28 d)  EOT a,b Notes					Notes					
	D1	D15	D22	D29	D36	D1	D15				
Adverse Event Ro	portin	g									
Monitor for Nonserious Adverse Events		All nonserious adverse events must be collected starting with the first dose of study drug and for a minimum of 100 days after discontinuing study treatment.									

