The dose of nivolumab and ipilimumab will be determined by safety data from Part 1C, and the dose of BMS-986253 will be determined by the totality of Part 1 data. If safety is confirmed in Cohort 1C1, for the first 12 weeks, participants will receive ipilimumab 3 mg/kg Q3W IV (4 doses), nivolumab 1 mg/kg Q3W IV (4 doses), and BMS-986253 3600 mg Q2W or placebo IV (given at Q2W frequency for 6 doses). After 12 weeks, participants will be maintained on BMS-986253 3600 mg Q2W or placebo IV (Q2W) and nivolumab IV (480 mg Q4W).

Approximately participants will be included in Part 2 and randomized in a 1:1 ratio to each arm.

Figure 5.1-2:Study Design Part 1

[figure not shown]
Protocol Amendment No.: 07

Date: 17-May-2024

74

Protocol Amendment No.: 07

Figure 5.1-3: Study Design Part 2

Abbreviations: BRAF, proto-oncogene B-Raf; CTLA, cytotoxic T-lymphocyte-associated protein; IL, interleukin, Ipi, ipilimumab; LDH, lactate dehydrogenase; Nivo, nivolumab; PD-(L)1, programmed cell death (ligand) 1; QXW, every X weeks.

c After 12 weeks, nivolumab will be administered at 480 mg Q4W.

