# 5.1.5 Follow-up

# 5.1.5.1 Safety Follow-up Period

Upon completion of study therapy (or up to a maximum of 156 weeks if applicable), or once the decision is made to discontinue the participant from treatment, ie, at end of treatment (EOT), all participants will enter a safety follow-up period.

For participants who complete all scheduled cycles of therapy, the EOT visit will be the same visit as the last scheduled and completed on-treatment visit, and will be the start of the safety follow-up period. For participants who do not complete all scheduled cycles of therapy, the EOT visit will be the next visit following the last study dose. If the EOT visit occurs 30 days or more after receipt of the last dose, then the EOT visit and Follow-up 1 visit can be completed at the same time.

All participants will be evaluated for any new AEs for a minimum of 100 days after discontinuing study treatment. Follow-up visits should occur at Days 30 and 100 ( $\pm$  7 days for all study visits) after the last dose. All participants will be required to complete the 3 clinical safety follow-up visits, regardless of whether new anti-cancer therapy is started, except those participants who withdraw consent for study participation.

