Any request to unblind a participant for non-emergency purposes should be discussed with the BMS Study Director/Medical Monitor (or designee).

In case of an emergency, the investigator(s) has unrestricted access to randomization information via the IRT and is capable of breaking the blind through the IRT system without prior approval from Sponsor. Following the unblinding, the investigator shall notify the Medical Monitor and/or study director.

Designated staff of Bristol-Myers Squibb Company may be unblinded prior to database lock to facilitate the bioanalytical analysis of pharmacokinetic samples and immunogenicity. Bioanalytical scientists in the Bioanalytical Sciences department of Bristol-Myers Squibb Company (or a designee in the external central bioanalytical laboratory) may be unblinded to (may obtain) the randomized treatment assignments in order to minimize unnecessary bioanalytical analysis of samples.

If a participant is assessed by the investigator to have disease progression, and unblinding is considered necessary to inform the appropriate subsequent anti-cancer therapy, the study treatment assignment for the participant can be obtained by the investigator through IRT for non-emergency unblinding. The investigator should follow the procedures outlined in the IRT manual to obtain the participant's study treatment assignment. The BMS central study team (including but not limited to clinical, statistics, data management) will remain blinded to treatment assignment.

The study will remain blinded until the database lock for as as described in the statistical analysis plan. If an interim analysis is conducted, the Sponsor may be unblinded

Protocol Amendment No.: 07

to the results after accrual to the study has completed and if the primary endpoint is met (as per Section 10).

Once the database lock for the final analysis is completed, the Sponsor and Investigators will be unblinded to treatment assignments; participants on the control arm will no longer receive placebo and will no longer have study visits on Day 15 of each cycle. Similarly, if BMS-986253 is discontinued for any participants (in accordance with Sections 7.6.1, 7.6.4, or 8.1), they will no longer have study visits on Day 15 of each cycle.

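### From Cycle 3 on, Table 2-6 schedules no vital signs at the Day 15 visit, where BMS-986253 or placebo alone is infused

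*Combined protocol and SAP*

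**What the plan says.** Section 9.1.2 gives a general rule: "Pre and post dose vital signs will be obtained during the dosing visits". It then says that vital signs are taken at selected times and points to the Schedule of Activities for those times. Section 9.1 does the same for all safety assessments.

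In Table 2-6 the vital signs row is marked at Days 1, 15, 22 and 29 of Cycles 1 and 2, at Day 1 from Cycle 3, and at end of treatment. Day 36 of Cycles 1 and 2 and Day 15 from Cycle 3 are blank. The Notes ask for pre- and post-dose readings on Day 1 of each cycle and add: "Post dose vital signs are to be taken after nivolumab infusion, ipilimumab infusion and BMS-986253 or placebo infusion".

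Dosing goes on at Day 15. Section 5.1 states for Part 2 that after 12 weeks "participants will be maintained on BMS-986253 3600 mg Q2W or placebo IV (Q2W) and nivolumab IV (480 mg Q4W"; the Protocol Summary gives the same maintenance schedule for Cohort 1C1. Section 7.5.2 ties the Day 15 visit to this infusion: once the database is locked for the final analysis, "participants on the control arm will no longer receive placebo and will no longer have study visits on Day 15 of each cycle".

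Table 2-4 (Cohorts 1B4 to 1B6) covers the same agent every 2 weeks: "BMS-986253 will be administered on day 1 and 15 of ALL cycles". Its vital signs row is marked at Day 15 in every cycle, including Cycle 5 and beyond.

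**The concern.** Section 9 makes adherence to the Schedule of Activities mandatory, so a site will normally work from the table. A site that follows the blank cell takes no scheduled vital signs at one of the two infusion visits in each cycle from Cycle 3. At that visit the experimental agent or its placebo is the only infusion.

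Section 7.6.6 lists fever, hypotension and hypertension among the possible signs of an infusion reaction. A same-day reading before the infusion makes such signs easier to judge. Without it, the site has to compare with a value from an earlier visit. What is at stake is a small loss in safety monitoring, not a loss of information for the efficacy comparison.

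**Working it through.** **Step 1: dosing days.** Table 2-6 has 42-day cycles for Cycles 1 and 2 and 28-day cycles after that. Dosing every 2 weeks falls on Days 1, 15 and 29 of a 42-day cycle, so 2 × 3 = 6 doses in 12 weeks. This reproduces the 6 doses that Section 5.1 states. In a 28-day cycle it falls on Days 1 and 15. The nivolumab row of Table 2-6 is marked at Days 1 and 22 in Cycles 1 and 2 and at Day 1 from Cycle 3. The ipilimumab row is marked at Days 1 and 22 of Cycles 1 and 2 only.

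**Step 2: dosing days against vital signs marks in Table 2-6.**

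| Visit | Infused | Vital signs marked |
|---|---|---|
| Cycles 1–2, Day 1 | nivolumab, ipilimumab, BMS-986253/placebo | yes |
| Cycles 1–2, Day 15 | BMS-986253/placebo only | yes |
| Cycles 1–2, Day 22 | nivolumab, ipilimumab | yes |
| Cycles 1–2, Day 29 | BMS-986253/placebo only | yes |
| Cycles 1–2, Day 36 | none | no |
| Cycle 3+, Day 1 | nivolumab, BMS-986253/placebo | yes |
| Cycle 3+, Day 15 | BMS-986253/placebo only | **no** |

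Up to the last line, vital signs are marked exactly when something is infused. In Cycles 1 and 2 the BMS-986253/placebo infusion alone is enough for a mark; from Cycle 3 it is not.

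**Step 3: is the blank a reading error?** Probably not. The row has eight cells for the eight columns, and neighbouring rows such as weight and physical examination fall on sensible days under the same headers. The BMS-986253/placebo administration row is not visible in the available text of Table 2-6. The dosing days above therefore rest on the every-2-weeks schedule in the table title and Section 5.1, and on Section 7.5.2.

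**Step 4: comparison with Table 2-4.** In 28-day cycles with doses on Days 1 and 15, Table 2-4 marks vital signs on 2 of 2 infusion days in every cycle. Table 2-6 marks 1 of 2 from Cycle 3.

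**Step 5: count of unmarked infusions, assuming uninterrupted dosing.** For week W from 12 on, the number of 28-day cycles is (W − 12)/4. Infusions = 6 + 2 × cycles; unmarked = 1 × cycles.

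| Week | 28-day cycles | Infusions | Unmarked | Share |
|---|---|---|---|---|
| 12 | 0 | 6 | 0 | 0% |
| 24 | 3 | 6 + 6 = 12 | 3 | 25% |
| 52 | 10 | 6 + 20 = 26 | 10 | 38% |
| 156 | 36 | 6 + 72 = 78 | 36 | 46% |

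Week 156 is the maximum treatment period named in Section 5.1.5.1. Under the Table 2-4 pattern the unmarked count is 0 at each of these times.

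**The case against.** The strongest reply is that there is no contradiction. Section 9.1.2 hands the timing to Section 2, and the Notes in both tables limit paired pre- and post-dose readings to Day 1. Table 2-4 therefore does not meet the dosing-visit sentence word for word either. This stands. A reader might infer that Table 2-6 violates a requirement for paired readings at every dosing visit, but the documents do not support that.

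The blank may also be deliberate, as a lighter maintenance visit. No visible assessment row with visit marks in Table 2-6 is marked at Day 15 from Cycle 3. Most of those rows, however, were never marked at Day 15 in Cycles 1 and 2. Only the concomitant medication row drops out in the same way. Table 2-4 does lighten its Day 15 visits from Cycle 3 (performance status, ECG and laboratory tests lose their marks), yet it keeps vital signs there. So a deliberate blank is possible but not shown, and no note explains it.

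The note on post-dose readings could be read as covering every infusion, including Day 15. It could equally be an explanation of the Day 1 rule, as the parallel note in Table 2-4 appears to be: "post dose vital signs are to be taken after BMS-986253 infusion AND after Nivolumab infusion". Sites may read it either way.

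Finally, a reader might infer that participants are infused at Day 15 without monitoring. The documents do not support that. Adverse events are collected continuously, Section 7.6.6 sets out bedside monitoring of infusion reactions, and Section 9 allows further measurements when clinically indicated.

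**Conclusion.** The point holds as a minor inconsistency in the schedule. From Cycle 3, Table 2-6 leaves up to 1 of 2 infusion visits per cycle without scheduled vital signs. This is out of line with its own Cycles 1 and 2 and with Table 2-4, and it sits poorly with the general sentence in Section 9.1.2.

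The cumulative shares assume uninterrupted dosing, and the 156-week figure is an upper bound that few may reach. Nobody who stops by week 12 is affected. In Part 2 the gap also ends for a participant whose BMS-986253 is stopped, and for the control arm when placebo ends at the final-analysis database lock.

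A reader might infer harm to the trial's results. There is none to claim: Section 9.1 counts vital signs among the safety assessments, but they are not a listed endpoint, and Section 10.3.2 lists only adverse event and laboratory analyses. Confidence is moderate, because the blank may be intended and part of Table 2-6 is not visible.

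**What to change.** In Table 2-6, mark vital signs and oxygen saturation at Day 15 of Cycle 3 and beyond for as long as BMS-986253 or placebo is being infused, and specify in the Notes at least a reading before the infusion. Section 9.1.2 can stay as it is.

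The change is one cell and a short note, made by administrative letter or with the next amendment. For participants and sites it adds one brief measurement at a visit that already takes place. A note saying only that the blank is intended would remove the ambiguity, but it would not provide the reading.
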